#### 7.2.2 Baseline Assessment and Randomization

#### **Baseline Assessments**

For participants who have successfully been screened for eligibility and are enrolled into the study, baseline assessments will be performed during February of each study year. Prior to the high DDS season, each eligible patient will:

- a) Answer a questionnaire regarding socio-demographic characteristics
- b) Provide detailed medical and medication history
- c) Household characteristics assessment

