# **Design, Interventions and Outcomes**

Type of study: Public Health Intervention Study

Intervention: Patients with AF will be recruited and will be randomized during the high DDS outbreaks season (Spring 2019 and 2020) with 1:1:1 ratio into three parallel groups to receive:

- a) No intervention for DDS.
- b) Intervention for outdoor exposure reduction, by reducing the time spend outdoors and by avoiding physical activity.
- c) Interventions for outdoor (as above) and indoor exposure reduction (by minimizing home ventilation and filtering indoor air).

Disease-related adverse health outcomes will be assessed in the three parallel arms of the study.

Approaches for delivering the intervention:

• A bidirectional, patient-centered e-Platform will be developed in order to facilitate prompt communication with the participants and provide early warnings regarding forecasted

upcoming DDS events through text messaging and smartphone applications. Furthermore, the same IT platform and mobile application will be utilised for the dissemination of the exposure reduction guidelines that the participants will follow, depending on which arm of the study they have been randomised to.

Assessment of adherence to intervention:

- Monitor compliance to exposure-reduction guidelines using remote sensors. The intervention for outdoor exposure reduction, entailing reduction of the time spend outdoors and avoidance of physical activity, will be assessed with the use of smart wristwatches that will have a global position system (GPS) and an accelerometer.
- The intervention for indoor exposure reduction, entailing minimization of home ventilation and filtering of indoor air, will be assessed with the use of particle samplers that will be placed outside and inside of houses and school classrooms.

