# Duration

Duration of the study: A feasibility (pilot) trial and refinement of protocols and tools will be performed during the high DDS outbreaks season of 2018. During the fall of 2018 and 2019, MEDEA personnel will initiate the recruitment procedure to enrol eligible AF patients for the two

main study periods (high DDS outbreaks season of February to May 2019 and 2020). Data collection, data cleaning and statistical analysis will take place in 2020.

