# 4 STUDY DESIGN

Type of study: Randomized clinical trial (Behavioural Intervention)

Patients with AF will be recruited during DDS outbreaks and will be randomized into three parallel groups to receive:

- a) No intervention for DDS,
- b) Intervention for outdoor exposure reduction, and
- c) Interventions for both outdoor and indoor exposure reduction.

Disease-related adverse health outcomes will be assessed in all the parallel arms of the study.

Previous publications of the MEDEA partners (Achilleos et al, 2014; Gerasopoulos et al, 2006; Krasnov et al, 2014), indicated that 2/3 of each year's DDS events in the Eastern Mediterranean region appear during February-May, with 10-15% of the days during this period being "DDS days". Thus we will perform this public health intervention study during February–May of 2019 and 2020.

Study population and location: Men and women with prior implantation of a dual lead (atrial and ventricular) pacemaker or ICD, will be recruited from the cardiac arrhythmia clinic at the Nicosia General Hospital of Cyprus (n=156) in project years 2018-2019 and 2019-2020. Each patient will have assessment of health outcomes during only one high DDS period.

Duration of the study: A feasibility trial and refinement of protocols and tools will be performed in the high DDS period of 2018. In the fall of 2018 and 2019, MEDEA personnel will start recruitment efforts to detect eligible AF patients for participation in the study during the high DDS periods of February-May 2019 and 2020.

Assessment of health outcomes:

- The occurrence of AF/ventricular arrhythmia episodes will be recorded daily using the already implanted participants' pacemakers or ICD during the 4-month study period. The recorded episodes will be downloaded with interrogation of the pacemaker or ICD during a visit to the Arrhythmia Clinic after the end of the study period.
- Phone interviews every 1 month throughout the high DDS outbreaks season will be carried out. Data collected will include symptoms of fatigue, change in medication use and unscheduled visits to health professionals for heart arrhythmias/episodes.
- Continuous recordings of biological parameters (pulse rate, pulse rate variability and temperature) obtained by wearing smart watch sensors and uploaded on line to the secure e-platform.

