# 6 STUDY INTERVENTIONS

# 6.1 Interventions, Administration, and Duration

Following recruitment, we will randomize participants with a 1:1:1 ratio to three parallel groups to receive:

a) no intervention for DDS

b) intervention for outdoor exposure reduction, by reducing the time spend outdoors and by avoiding physical activity

c) interventions for outdoor (as above) and indoor exposure reduction (by minimizing home ventilation and filtering indoor air).

In the indoor intervention arm of the study, exposure reduction measures will be applied in the patient's household/bedroom settings.

After randomization, and prior to the high DDS season, each eligible participant will complete a questionnaire, providing socio-demographic characteristics, detailed medical and medication history, and will be trained in the tools and procedures to be followed during the monitoring sessions while in the community. The study design offers also the opportunity to assess:

- outdoor exposures to PM,
- indoor exposures to PM and
- related health outcomes in three parallel groups during the same DDS events with and without intervention measures (Figure C8.1).

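### Recruitment, randomisation, baseline and training are placed both before and within the February–May season, and the start of the AF-burden window is not fixed

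*Protocol*

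**What the plan says.** The Protocol Summary (Duration) defines the "high DDS outbreaks season of February to May 2019 and 2020". Against that definition, the start-up steps are placed as follows.

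- **Recruitment.** Section 4: "Patients with AF will be recruited during DDS outbreaks and will be randomized into three parallel groups". The Summary (Duration) and section 7.2.1 instead place recruitment and screening in the preceding autumn.
- **Randomisation.** The Summary (Design, Interventions and Outcomes) says that patients "will be randomized during the high DDS outbreaks season (Spring 2019 and 2020) with 1:1:1 ratio". Section 6.1 puts it earlier: "After randomization, and prior to the high DDS season, each eligible participant will complete a questionnaire". Section 7.2.2 ties it only to completion of the eligibility check and gives no date.
- **Baseline.** Section 7.2.2 states that "baseline assessments will be performed during February of each study year" and continues "Prior to the high DDS season, each eligible patient will", followed by the list of assessments.
- **Training.** Section 6.1 puts it in the same step as the questionnaire, after randomisation: participants "will be trained in the tools and procedures to be followed during the monitoring sessions".

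The Summary and section 2.1 define AF burden as the share of time in AF over an observation period. The Summary calls the recording period four months long. Neither gives a first day. The schedule in section 7.1 has a baseline column and a final column at four months, with 30 days' leeway either way. Sections 7.2.3 and 7.2.4 set the mid-point in April and the end-point in May. The SAP adds nothing on when the window begins.

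**The concern.** A season that begins in February cannot also begin after a baseline held during February, and randomisation cannot be both before and during it. The conflict matters because it bears on time zero of the primary outcome. A patient cannot follow the dust-alert instructions until randomised and trained. The implanted device records throughout and is downloaded once, after monitoring ends, so days before training may be on file. No rule in either document excludes them. If they are counted, time in which the arms are treated alike is averaged into the comparison and pulls the difference towards zero.

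There is a second, smaller issue. Section 6.1 has the baseline questionnaire completed after allocation. Participants learn their arm from the instructions they receive, so their answers could differ by arm.

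**Working it through.** **Inputs.** Season February to May (Protocol Summary). Dust days make up 10–15% of season days (Protocol section 4). Control burden 15% with SD 15, 20% relative reduction, 108 versus 216 patients, two-sided Mann-Whitney-Wilcoxon test at 0.05, alternative WeibullMS(15 15) versus WeibullMS(12 15), stated power 81% (SAP section 1). Protocol section 8.1 prints a different alternative, with both groups at WeibullMS(15 15). That is a separate matter, and the SAP version is used here.

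**1. The plan's own figures.** 20% of 15 is 3.0 points, and 0.03 × 1,440 = 43.2 minutes per day, which agrees with the stated 43. Weibull variates were solved for the stated means and SDs: shape 1.00 and scale 15.0 for control, shape 0.806 and scale 10.65 for intervention. With 10,000 to 20,000 replicates, power is 76%, not 81%. The dilution figures below therefore start from 76%.

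**2. Share of the window before the intervention.** The documents state no figure. For a calendar window from 1 February to 31 May:

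- 2019: 28 + 31 + 30 + 31 = 120 days. A start at the end of February loses 28/120 = 23.3%.
- 2020: 29 + 31 + 30 + 31 = 121 days. A start at the end of February loses 29/121 = 24.0%.
- Randomisation and training complete before 1 February, or a window counted from randomisation: 0%.
- A start after February, which the Summary's wording on randomisation would allow: more than 24%.

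**3. Illustrative dilution.** Diluted difference = 3.0 × (1 − d/120) for a delay of d days. This assumes no effect before the start, an effect spread evenly afterwards, the same delay for every patient, SD held at 15, and the planned 20% applying only to time after the start.

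| Delay (days) | Difference (points) | Simulated power |
|---|---|---|
| 0 | 3.00 | 76% |
| 7 | 2.83 | 71% |
| 14 | 2.65 | about 65% |
| 28 | 2.30 | about 52% |

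Repeat runs differ by about one percentage point.

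**4. What the even-spread assumption hides.** The instructions are sent when a dust event is forecast. At 10–15% of 120 days there are 12 to 18 dust days per season. The loss depends on how many of these fall before a patient's start. The documents give no distribution by month, so it could be below or above the proportional figure.

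**5. Does counting from baseline settle it?** Only in part. A late-February baseline plus four months ends in late June, beyond both the season and the May end-point. Stopping in May leaves about three months for late starters. The 30-day leeway in section 7.1 permits either, so windows of different length and dust content remain open.

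**The case against.** The strongest reply is that neither document says pre-intervention days are counted. The schedule can be read as four months from baseline. Autumn screening, randomisation once eligibility is settled, and training before the season together give a loss of zero. This stands as one permissible reading. It does not remove the problem, because it sets aside the Summary's in-season randomisation, section 4's recruitment during outbreaks and section 7.2.2's February baseline.

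A reader might infer that a quarter of the measured AF burden precedes the intervention. The documents do not support that. The 23–24% is a share of observation time, not of burden. It requires a calendar window and a start at the very end of February, and it is not a maximum if starts run later. Starts would also probably be staggered through the month, so the 28-day row is severe for the group as a whole.

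A reader might also infer that section 7.2.2 expressly puts baseline before randomisation. Only the order of its headings suggests so. The harm from a questionnaire completed after allocation is limited, because section 7.2.1 already collects a demographic, medical, medication and symptom survey at screening and the primary outcome is device-recorded.

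**Conclusion.** The point holds as an internal contradiction about time zero of the primary outcome, together with an undefined window start. Followed as written, the Summary's randomisation wording, the February baseline and the May end-point can count pre-intervention days as intervention time. The size is conditional: 0% on some readings, up to about 23–24% of observation time if start-up runs through February within a calendar window, and more if it runs later. The fall in power from 76% to about 65% or 52% illustrates sensitivity under the assumptions listed and is not a forecast. The gap between the simulated 76% and the stated 81% is a separate matter and does not arise from timing. The questionnaire order is secondary. The contradiction should be corrected; confidence is medium, because the loss depends on which reading the sponsor intended.

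**What to change.** - Reconcile the Summary and sections 4, 6.1, 7.1 and 7.2.2 on when recruitment, randomisation, baseline and training take place relative to the season.
- State in the Protocol and SAP that the primary AF-burden window starts no earlier than randomisation and training, with start and end set by the same rule in all arms. One option is a prespecified calendar date per site and season by which both steps are to be complete. Waiting for the last patient at a site is not essential, and would let one late enrolment remove dust days for everyone.
- Use device recordings from before the window as the baseline burden value. Section 5.1 requires implantation at least two months before randomisation, so such recordings should exist. The documents do not say how far back the download reaches, and this should be confirmed.
- Complete the baseline questionnaire before allocation is disclosed, which reverses the order in section 6.1.

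The cost is mainly wording, although it does define the primary endpoint window and so belongs in both documents. The downside is that some early-season days, possibly including dust days, may leave the primary window if enrolment runs late.

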#### Randomization

Following the eligibility assessment, participants will be randomized using PASS 14 software that allows for random number generation. Randomization will be carried out with a 1:1:1 ratio to three parallel groups:

- a) Control group A: No intervention for DDS,
- b) Intervention group B: Intervention for outdoor exposure reduction, and
- c) Intervention group C: Intervention for outdoor and indoor exposure reduction (patient's household/bedroom settings)
- 7.2.3 Follow-up Assessments
  - Intervention mid-point assessment April 2019/2020:
    - Current medications
    - Intervention discontinuation
    - Telephone questionnaire
    - Daily recordings of AF/ventricular arrhythmia episodes
    - Continuous recordings of biological parameters (pulse rate, pulse rate variability, temperature)
    - Adverse events

#### 7.2.4 Completion/Final Evaluation

- Intervention end-point assessment May 2019/2020:
  - Current medications
  - Intervention discontinuation
  - Telephone questionnaire
  - Daily recordings of AF/ventricular arrhythmia episodes
  - Continuous recordings of biological parameters (pulse rate, pulse rate variability, temperature)
  - o Adverse events

### 8 STATISTICAL CONSIDERATION AND ANALYSIS PLAN

We will build a spatial-temporal individual-based database to continuously collect air quality and meteorological information along with the patient's heart rate assessments. This unique database will enable a valid analysis of an impact of DDS on heart rate variation.

#### 8.1 Sample size consideration

There are no studies that evaluated the reduction in AF burden attributed to reduction in exposure to ambient air pollution.

We assume that the mean AF burden in the control group will be 15%+/-15%. We conservatively estimated the expected intervention effect to be 20% of relative reduction in AF burden. This is translated into the reduction of AF burden by mean of 43 minutes per 24 hours.

Group sample sizes of 108 and 216 achieve 81% power to show a difference in means when there is a difference of -3.0 between the null hypothesis mean difference of 0.0 and the actual mean difference of 3.0 at the 0.05 significance level (alpha) using a two-sided Mann-Whitney-Wilcoxon Test. These results are based on 2000 Monte Carlo samples from the null distributions: WeibullMS(15 15) and WeibullMS(15 15), and the alternative distributions: WeibullMS(15 15) and WeibullMS(15 15).

#### 8.2 Statistical analysis

#### 8.2.1 Descriptive statistics

Summaries of main variables will be presented in form of means and standard deviations for normal distributed quantitative variables, medians and ranges for non-normal distributed quantitative variables, distribution in percentages for qualitative variables.

### 8.2.2 Univariate analysis

Univariate analysis will be mostly used for analysis initial datasets consisted of personal data records.

The method of analyses for continuous variables will be parametric using Paired and Unpaired ttest and Repeated Measurements ANOVA.

Non-parametric procedures will be used if parametric assumptions could not be satisfied, even after data transformation attempts. These tests will include Mann-Whitney, Wilcoxon and Spearman Correlation tests.

Categorical variables will be tested using Chi-Square test.

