Mitigating the Health Effects of Desert Dust Storms Using Exposure-Reduction Approaches (MEDEA) project

Assessment of health outcomes in children with asthma (ACTION C.7) and in adults with atrial fibrillation (ACTION C.8) during DDS events (with vs without intervention measures)

Public Health Intervention Study

Statistical Analysis Plan

(April 2018)

1. Sample Size Determination and Power Calculations

Sample size calculations for the panel study of asthmatic children

Sample size calculations are based on expected changes in asthma symptoms measured by asthma control test (ACT), which is our primary health outcome. Childhood ACT has seven items and provides a score ranging from 0 (poorest asthma control) to 27 (optimal asthma control). A cut-off point of 19 indicates uncontrolled asthma. Previous studies have shown that a minimally meaningful change in the ACT score is ranging from 2 to 3 points (Voorend-van Bergen et al, 2014). To detect a statistically significant difference of 3 points, the minimum sample size needed in each of the 3 groups is 100 participants. This sample size calculation is assuming a level of 0.05 and a power of at least 80% to detect this difference between the comparison groups.

Sample size calculations for the panel study of atrial fibrillation (AF) patients

There are no studies that evaluated the reduction in AF burden attributed to reduction in exposure to ambient air pollution.

We assume that the mean AF burden in the control group will be 15%+/-15%. We conservatively estimated the expected intervention effect to be 20% of relative reduction in AF burden. This is translated into the reduction of AF burden by mean of 43 minutes per 24 hours. Group sample sizes of 108 and 216 achieve 81% power to show a difference in means when there is a difference of -3.0 between the null hypothesis mean difference of 0.0 and the actual mean difference of 3.0 at the 0.05 significance level (alpha) using a two-sided Mann-Whitney-Wilcoxon Test. These results are based on 2000 Monte Carlo samples from the null distributions: WeibullMS(15 15) and WeibullMS(15 15), and the alternative distributions: WeibullMS(15 15) and WeibullMS(12 15).

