Summaries of main variables will be presented in form of means and standard deviations for normal distributed quantitative variables, medians and ranges for non-normal distributed quantitative variables, distribution in percentages for qualitative variables.

Univariate analysis

Univariate analysis will be mostly used for analysis initial datasets consisted of personal data records.

The method of analyses for continuous variables will be parametric using Paired and Unpaired t-test and Repeated Measurements ANOVA.

Non-parametric procedures will be used if parametric assumptions could not be satisfied, even after data transformation attempts. These tests will include Mann-Whitney, Wilcoxon and Spearman Correlation tests.

Categorical variables will be tested using Chi-Square test.

Multivariate analysis

We will apply 2 modelling strategies:

Case- Crossover design

The association between DDS events and episodes of cardiac arrhythmia will be assessed in a casecrossover design ⁽¹⁰⁾. This method has been used previously to study triggers of acute cardiovascular events ⁽¹¹⁾. We will define case periods by the time of each confirmed episode of cardiac arrhythmia, rounded to the nearest hour. We will match control periods on weekday and hour of the day within the same calendar month. Conditional logistic regression analysis will be performed to analyze the exposure odds ratio with 95% confidence intervals on risk of cardiac arrhythmia.

Hierarchical model

Generalized Linear Model will be used to fit a Poisson regression of daily AF episodes against temporal variables and DDS data based in hierarchical model. Data model with random effect include repeated episodes of AF in each patient, the intervention groups and the 3 sites of the research. Date model with fixed effect include DDS event during the period of the study.

Analysis will be performed using R Project for Statistical Computing version 3.0 or higher and IBM SPSS software version 23 or higher.

3. References

Voorend-van Bergen S, et al. Monitoring childhood asthma: web-based diaries and the asthma control test. J Allergy Clin Immunol. 2014;133:1599-605.

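### The 81% power is claimed for a difference in means but comes from a rank test that no section assigns to the primary comparison; it is about 76% for the rank test and about 39% for the 3-point mean

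*Protocol*

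**What the plan says.** **Sizing.** Protocol 8.1 sets the control group out plainly: "We assume that the mean AF burden in the control group will be 15%+/-15" percent. On the effect it says: "We conservatively estimated the expected intervention effect to be 20% of relative reduction in AF burden". It converts this to 43 minutes per 24 hours. The power claim is: "Group sample sizes of 108 and 216 achieve 81% power to show a difference in means". SAP section 1 repeats it, "at the 0.05 significance level (alpha) using a two-sided Mann-Whitney-Wilcoxon Test". The two documents differ in the alternative used for the simulation. The SAP has Weibull mean/SD 15/15 against 12/15; the Protocol prints 15/15 for both groups.

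**Primary comparison.** Protocol 2.1 compares the two intervention groups combined with control on AF burden, a percentage of time. It names no test.

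**Test rule.** Protocol 8.2.2 says: "The method of analyses for continuous variables will be parametric using Paired and Unpaired ttest and Repeated Measurements ANOVA". It then adds: "Non-parametric procedures will be used if parametric assumptions could not be satisfied, even after data transformation attempts". Mann-Whitney is among the procedures listed. The SAP's univariate section has the same rule: "The method of analyses for continuous variables will be parametric using Paired and Unpaired t-test and Repeated Measurements ANOVA". The Protocol section opens by saying that univariate analysis is chiefly meant for the first sets of individual records.

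**Models.** In its part on AF patients, the SAP says that the preceding equations, set out for the asthma panel, will quantify benefit on primary and secondary outcomes. The case-crossover and Poisson models in both documents concern arrhythmia episodes, not burden.

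**The concern.** Three things do not line up.

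- The power sentence attaches a rank test's power to a mean difference. Under the SAP's distributions the two groups differ in shape as well as mean, so the rank test responds to more than the 3-point shift in means.
- The sized test stands last in the only written order for comparing two groups on a continuous outcome, and no section lifts AF burden out of that order.
- The order has no decision criterion: no named check, threshold or list of transformations. A second route, the mixed model, is also open for the same outcome.

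The test and scale for the primary result would thus be chosen with outcome data in hand, and neither document describes masking of whoever makes that choice. Readers would also take 81% as the chance of showing the 43-minute mean reduction, which the design does not offer.

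**Working it through.** **Inputs.** Control mean 15, SD 15; effect 3 points (20% of 15), and 0.03 × 1440 = 43.2 minutes per day; two-sided 5% (Protocol 8.1, SAP section 1). Intervention mean 12, SD 15 (SAP section 1). Groups of 108 and 216, read as control against the two intervention arms pooled, from the 1:1:1 allocation and Protocol 2.1. Assumption: WeibullMS(a b) means mean a and SD b.

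**Step 1. Distributions.** For a Weibull, mean = λΓ(1+1/k) and (SD/mean)² = Γ(1+2/k)/Γ(1+1/k)² − 1.

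- Control: SD/mean = 1, so k = 1.000 and λ = 15.
- Intervention: SD/mean = 1.25, so k = 0.806 and λ = 10.65.
- Medians, λ(ln 2)^(1/k): 10.4 and 6.8. The mean falls by 20%, the median by about 35%.

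**Step 2. The plan's own figure.** Simulating the two-sided Mann-Whitney test on these inputs (40,000 trials) gives 76.3%, not 81%. The plan used 2,000 samples, for which the 95% Monte Carlo margin is 1.96 × √(0.81 × 0.19/2000) = 1.7 points, so chance does not explain the gap of 4.7 points. An approximate formula for the Weibull shape gives 80.8%, but with an intervention SD of 15.4 rather than 15; this may be the source of 81% but cannot be confirmed. The Protocol's printed alternative, 15/15 in both groups, gives about 5%, the type I error rate.

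**Step 3. A test of the mean.**

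- SE = 15 × √(1/108 + 1/216) = 1.77; 3/1.77 = 1.70.
- Power ≈ Φ(1.70 − 1.96) = 39.6%; noncentral t, 39.4%; simulated, 39.7% pooled and 38.6% Welch.
- Difference detectable with 81% power: (1.96 + 0.88) × 1.77 ≈ 5.0 points, or 72 minutes per day.
- Control patients needed for 81% power at 3 points, 1:2 allocation: about 303, against 606.
- Half-width of the 95% CI for the mean difference: 1.96 × 1.77 = 3.5 points, about 50 minutes per day, wider than the planned effect.

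**Step 4. Power by test, same inputs.**

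| Test | Power |
|---|---|
| t-test, untransformed | 39–40% |
| t-test, square root | 65–66% |
| t-test, cube root | 72–73% |
| t-test, log(x+1) | 76–78% |
| t-test, log (undefined at zero burden) | 80–83% |
| Mann-Whitney | 76% |

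In about 38% of simulated trials Mann-Whitney was significant and the untransformed Welch test was not.

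**Step 5. The 8.2.2 sequence as a whole.** The documents name no check, so Shapiro-Wilk at 5% is assumed.

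- Residual check on raw, log and square-root data: the sequence ended in Mann-Whitney in 4,000 of 4,000 trials, with power about 76%.
- Check in each group, with cube root and log(x+1) also allowed: raw data were rejected in practically every trial. The sequence ended in Mann-Whitney in about 76% of trials, a cube-root t-test in 22% and a log(x+1) t-test in 2%. Overall power was 76.1%, against 76.0% for Mann-Whitney alone.

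**The case against.** A reader might infer that the t-test is the planned primary test and that the trial therefore has 39% power, about half of what it claims. The documents do not support that, for two reasons.

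First, 8.2.2 is a sequence. Its next sentence sends the analysis to Mann-Whitney when parametric assumptions cannot be met. Under the skewed distributions used for sizing, a formal normality check does not keep the raw t-test, and following the sequence costs essentially no power relative to Mann-Whitney. To stay with the raw t-test an analyst would have to argue that groups of 108 and 216 are large enough to ignore skewness. Nothing in the text forbids that argument, but nothing in the text makes it.

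Second, it is not established that 8.2.2 governs the primary comparison at all. Its opening sentence describes a narrower use, and the SAP points AF burden to the mixed-model equations.

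Both points stand, and they limit the 39% to two cases: the raw t-test is retained, or the mean difference is the target. They do not rescue the power sentence. If 8.2.2 does not govern, then nothing assigns the sized test to the primary comparison, and the mixed-model passage gives no hypothesis test for B and C combined against A.

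It can also be said that preferring a rank test is a choice of estimand, and that a mean-based analysis with revised sizing would serve the 43-minute effect directly. That is fair. It would need about 909 analysed patients (303 + 606) rather than 324, which is why the change below keeps the test on which the trial was sized.

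**Conclusion.** The point holds in this form: the primary test of AF burden is not fixed in advance, and the stated 81% power for a mean difference is not a property of the design. On the SAP's inputs, power at 108 v 216 is about 76% for Mann-Whitney and about 76% for the 8.2.2 sequence under a Shapiro-Wilk check. A test of the 3-point mean difference has about 39%. It does not follow that the plan as written has 39% power.

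The figures assume patient-level burden drawn from the stated Weibull distributions, no adjustment for site, no patients at exactly zero burden, and 324 patients analysed. The result for the sequence also depends on the normality check and transformations assumed, because the documents specify neither.

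**What to change.** 1. In Protocol 8.2 and SAP section 2, state that patient-level AF burden, B and C combined against A, is tested by the two-sided Mann-Whitney-Wilcoxon test used for sizing, with no normality check or transformation step. Exempt it expressly from the parametric-first rule.
2. Label the mixed model for AF burden, the case-crossover analysis and the Poisson model as supportive.
3. In Protocol 8.1 and SAP section 1, delete the claim about a difference in means. Restate the power as about 76% for the rank test under Weibull mean/SD 15/15 v 12/15, and add that a test of the 3-point mean difference has about 39%.
4. Reconcile the Protocol's alternative (15/15 in both groups) with the SAP's (15/15 v 12/15).
5. Report the mean difference in minutes per day with a bootstrap 95% CI as a supporting estimate.

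The cost is wording in both documents and a less favourable stated power, with no additional patients. The primary p-value will not refer to the mean in minutes, which is why item 5 is needed.
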